Finalize the d2c strategy The finalization activities will include: (1) refining data extraction protocols and developing a case management module within the MIS; (2) developing a report generation and dissemination protocol for each clinic and (3) specify clinic/implementation team structure, roles, and management plans based on findings from in-depth interviews.

Develop data extraction protocols and create case management module within MIS

The MIS is designed as an electronic medical record system, to be used by clinical providers for routine patient data management. It has centralized architecture, where all data are immediately uploaded to a national-level server. According to the feedback we received in our ART OPTI project, tracking and prioritization of out-of-care patients is one of the most requested features for the MIS. We will partner with the Public Health Center of the MoH, the government body responsible for HIV response and coordination of PEPFAR activities in Ukraine and owner of the MIS to create a module within the MIS that will: a) identify all HIV-positive PWID meeting the criteria of not-in-care [patients registered as HIV-positive who had no HIV medical visits in a calendar year]; b) provide a useful summary of all clinical information that will be needed for case managers [drug use, CD4, viral load, ART history, HIV care appointments made and kept, co-morbid diagnoses and medications, and MAT history]; and c) provide a portal for entry and export of case management data (referrals made, appointments kept, contact attempts, case management notes).

Specific Aim 2: To pilot a randomized clinical trial of a D2C strategy versus standard of care

Study Design

[figure not shown]
This pilot study is designed to test the performance characteristics and capabilities of study design, measures, procedures, recruitment criteria, and operational strategies that are under consideration for use in a prospective RCT. We will also assess feasibility of the RCT by measuring the key parameters for sample size calculation, namely the effect size and coefficient of variation.

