D2C is a structural intervention designed to sustainably change the HIV care providers' practices and facilitate information exchange at the facility level. To address the implementation science questions by measuring the provider-level outcomes and avoid contamination of the control condition due to unblinded allocation of intervention at the patient level, we propose a cluster-randomized trial design for this pilot study and the prospective RCT. We will select eligible HIV clinics (see "Study Sites," above) and randomly assign them 1:1 either to the intervention or the control arms. To achieve greater comparability between the arms, we will match pairs of eligible sites based on organizational context factors derived from Aim 1 data analysis, including facility size and type (e.g., NGO vs. public clinic), service delivery structure (e.g., social workers vs. nurses), and existing services for HIV-positive PWID (e.g. Steps Toward Health) and will randomize within the pairs. This will minimize the degree of between-cluster variation within the groups and increase power and precision.

Randomization will be conducted by the data manager using a computer program.

Sample size

We used methodology from Hayes et al⁸⁴ to determine the effect size that the intervention needs to demonstrate in a feasible matched-pair randomized trial. We assumed the cluster size of 75 patients (based on the optimal case manager workload) with 5 clusters per arm (potentially manageable number given the existing research infrastructure in Ukraine), coefficient of variation between clusters within matched pairs equal to 0.15 (empirically estimated based on the data from 56 clinics in the ART OPTI study, see Previous Studies), power of 80% and 0.05 significance level. Proportion of participants re-engaging into ART within 3 months after inclusion into the study was used as the key outcome. Under the assumptions, the relative difference between the study arms should be at least 22% (e.g. 50% vs 72%). The adjacent chart shows the power and sample size of a pilot trial needed to detect this difference with 0.05 significance level. To achieve 80% power, we will need to recruit 160 participants, or 80 per arm. We propose to divide the sample equally between 4 sites (2 per arm) to test the matching procedures. We do not adjust for loss-to-follow-up because for our main outcomes (ART initiation, viral suppression), loss to follow-up is equal to not achieving the outcome.

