We have powered this pilot study to evaluate feasibility of a prospective cluster RCT. The RCT will be considered feasible if the difference in the proportion of patients achieving the primary outcome (engagement in HIV care) will reach 22% between the study arms. We will estimate the impact of the intervention on the HIV care continuum using mixed effects models. For all outcomes, the data will have the same structure, with observations (t) nested within participants (i) nested within sites (j) nested within matched pairs (k). The correlations among observations will be addressed by using fixed-effects indicators for matched pair and normally distributed random intercepts for sites and for participants. Our mixed-effects models will include indicators for each of the two follow-up assessments, an indicator for site group assignment, and two group-assignment-by-follow-up interaction terms. We will also include sex/gender, age, and baseline covariates that have been identified in preliminary analyses as varying significantly across sites. A logit link function will be used for the primary outcome of ART (re-)initiation (defined above), and the coefficients for the two group-assignment-by-follow-up interaction terms will provide the estimates of the subject-specific intervention effects at 6 and 12 months post-baseline. We will examine the effects of sex/gender, age, substance use severity, ART history at baseline and other covariates in the multivariable models.

We will characterize patterns of behavior that impact HIV transmission (episodes of syringe sharing and episodes of unprotected intercourse in the prior 30 days without viral suppression) and we will use the same mixed-effects approach described above but with a log link function and negative

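### The 80% power stated for 160 participants does not hold for the pilot's matched-pair cluster design: about 12% on a pair-level test (1 df) and 45% even with the between-clinic variance known

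*Combined protocol and SAP*

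**What the plan says.** The study design text under Specific Aim 2 says the pilot will assess feasibility by "measuring the key parameters for sample size calculation, namely the effect size and coefficient of variation". It then commits the pilot itself to clusters: "we propose a cluster-randomized trial design for this pilot study and the prospective RCT", with clinics matched in pairs and randomised 1:1 within pairs.

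The sample size section first works out the effect that the later RCT should show. Its inputs are 75 patients per cluster, 5 clusters per arm, "coefficient of variation between clusters within matched pairs equal to 0.15", 80% power and a 0.05 level. The outcome is re-engagement in ART within 3 months, and the example is 50% vs 72%. The text calls this a 22% relative difference, but the example is 22 percentage points.

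For the pilot it refers to a chart (not reproduced in the text available) and states: "To achieve 80% power, we will need to recruit 160 participants, or 80 per arm". It continues: "We propose to divide the sample equally between 4 sites (2 per arm) to test the matching procedures". No allowance for clustering is attached to the 160.

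The section Statistical Analysis and Feasibility Assessment opens with "We have powered this pilot study to evaluate feasibility of a prospective cluster RCT". It then calls the RCT feasible if the difference in the proportion "achieving the primary outcome (engagement in HIV care) will reach 22% between the study arms". The planned mixed models use "fixed-effects indicators for matched pair and normally distributed random intercepts for sites and for participants".

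**The concern.** In a cluster-randomised trial, the precision of the arm comparison depends on between-clinic variation and on the number of clinics, as well as on the number of patients. The protocol allows for both when sizing the RCT. It then gives a pilot power that appears to use neither, in the same paragraph that divides the sample over four clinics. With a fixed effect for pair, 4 clinics less one parameter each for intercept, pair and arm leave 1 between-clinic degree of freedom.

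Two things are at stake. A reader of the protocol is told that the pilot can detect 50% vs 72% with 80% power. And that statement introduces the go/no-go rule for the RCT, so the rule looks better supported than it is.

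**Working it through.** **Inputs, all from the sample size section unless noted.** Control rate p0 = 0.50; intervention rate p1 = 0.72; difference 0.22; 160/4 = 40 patients per clinic; 2 pairs; CV k = 0.15; alpha 0.05, taken as two-sided because the protocol does not say; no allowance for dropout, because missing counts as failure.

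**1. The plan's own figure, treating patients as independent.** With the mean rate 0.61 under the null:

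- n per arm = [1.96·√(2·0.61·0.39) + 0.8416·√(0.25 + 0.2016)]² / 0.22² = 75.97, so 76.
- Power at 80 per arm is 82.0% (81.6% by exact enumeration of the uncorrected chi-square test).
- SE = √[(0.25 + 0.2016)/80] = 0.0751.

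So 80 per arm with roughly 80% power fits an unclustered calculation with some rounding up. With a continuity correction the requirement would be 85 per arm. The chart is not available, so the origin of 160 cannot be confirmed.

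**2. The design described.** The variance of one pair difference is [p0(1−p0) + p1(1−p1)]/40 + k²(p0² + p1²):

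- sampling part: (0.25 + 0.2016)/40 = 0.01129
- between-clinic part: 0.0225 × (0.25 + 0.5184) = 0.01729
- total 0.02858; over 2 pairs 0.01429; SE = 0.1195
- noncentrality 0.22/0.1195 = 1.84

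Power at these inputs:

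- pair-level t-test, 1 df (critical value 12.7): **11.6%**; two simulations of 400,000 runs gave 12.3% and 12.6%
- matching ignored, 2 df: 19.5%
- between-clinic variance treated as known: Φ(1.84 − 1.96) = **45%**
- one-sided versions of these three: 23%, 35% and 58%

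**3. Sensitivity.** For 50% vs 72%, by CV:

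| CV | 0 | 0.05 | 0.10 | 0.15 | 0.20 | 0.25 |
|---|---|---|---|---|---|---|
| 1 df | 18% | 17% | 14% | 12% | 10% | 9% |
| variance known | 83% | 77% | 62% | 45% | 33% | 25% |

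For CV 0.15 and a 22-point difference, by control rate:

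| Control rate | 10% | 20% | 30% | 40% | 50% | 60% |
|---|---|---|---|---|---|---|
| 1 df | 19% | 16% | 14% | 13% | 12% | 11% |
| variance known | 87% | 72% | 60% | 52% | 45% | 40% |

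Power comes near 80% only if the variance is treated as known and, in addition, the control rate is low or clustering is almost absent. Patient numbers are not the limit: with unlimited patients per clinic at CV 0.15, 1-df power is 15%. At 40 per clinic, 80% needs 7 pairs.

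**4. Check of the formula on the RCT inputs.** With 75 per clinic and 5 per arm, it gives 68% (4 df) to 90% (variance known), which brackets the protocol's 80%. The pilot's inputs give 12% to 45%.

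**5. The feasibility rule.** The chance that the observed difference reaches 22 points is 1 − Φ[(0.22 − d)/SE], with the SE recalculated for each true difference d. At control rate 50%:

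| True difference | Independent patients | CV 0.15 |
|---|---|---|
| 10 points | 6% | 15% |
| 22 points | 50% | 50% |
| 30 points | 87% | 74% |

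The rule applies to engagement in HIV care, for which the protocol gives neither a control rate nor a CV; the values used here belong to ART re-engagement. Over control rates of 20% to 60% and CVs of 0 to 0.25, the chance is about 4% to 25% at a true 10 points and 65% to 89% at a true 30 points.

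**The case against.** The strongest reply is that the 12% belongs to a test the protocol does not plan. The planned analysis is a mixed logistic model with pair fixed effects, site random intercepts, covariates and robust variances, and most of the fall to 12% comes from the 1-df critical value. That is fair as to the exact figure, and 12% should be labelled a benchmark with 45% beside it. It does not rescue the 80%. A large-sample Wald test from the mixed model would show about 45% nominal power, with an unreliable error rate at four clinics. A patient-level test that ignores clinics would reject about 72% of the time at 50% vs 72%, but with a type I error near 15% (simulated at 50% in both arms, CV 0.15).

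Second, the chart is not available and the unclustered origin of 160 is inferred. That is true, but the conclusion does not need the origin. The design and the CV are in the text, and no clustered calculation tried at 50% vs 72% with that CV reaches 80%.

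Third, this is a pilot, the four sites are there to test matching, and the feasibility rule uses a point estimate. This stands, and it limits the consequence: no significance test decides the pilot, and the even chance of passing at a true 22 points holds at any SE. But the protocol chose to claim 80%, and the claim is wrong for its design.

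Fourth, the pass probabilities borrow inputs from another outcome. This also stands, so they should be given as a labelled range.

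**Conclusion.** The concern holds. The 80% power claim does not describe the pilot as designed. At 50% vs 72%, CV 0.15, 2 pairs and 40 patients per clinic, power is about 12% on a pair-level test (1 df) and about 45% if the between-clinic variance were known. The SE is about 0.12, against 0.075 for independent patients. The figures assume a two-sided 0.05 test and that the CV stated for the RCT calculation, the only one in the protocol, applies to the pilot. On the 1-df test the conclusion needs no clustering at all, since power is 18% even at CV 0.

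The consequence is moderate. The false figure stands beside the rule that decides whether the RCT is feasible, but the rule itself does not use a p-value. This should be corrected; it does not call for a larger pilot.

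**What to change.** **Sample size section.** Delete the 80% power claim for the pilot and put in its place, for example: *With 2 matched pairs, 40 participants per clinic and a CV of 0.15, the SE of the difference for 50% vs 72% is about 0.12. Power is about 12% for a pair-level test (1 df, a benchmark for the mixed model with pair fixed effects), or about 45% if the between-clinic variance were known.* The sponsor should also give its own reason for 160, since the protocol offers none other than power.

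**Statistical Analysis and Feasibility Assessment.** Replace the opening statement that the pilot is powered with one that follows the stated design aim: the pilot provides estimates of the effect size and CV for planning the RCT, and effect estimates are descriptive. Add how the rule behaves: it is met about half the time at a true difference of 22 points, about 15% of the time at 10 points (range about 4% to 25%) and about 74% at 30 points (range 65% to 89%). Say that the central values assume a 50% control rate and a CV of 0.15, both taken from ART re-engagement. Add that the CV will be poorly estimated: with 1 df, a 95% chi-square interval for the between-clinic SD runs from roughly 0.45 to 32 times the estimate.

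**Cost.** Wording in two sections and a less favourable stated figure, with no extra enrolment. If the word descriptive is adopted, the preliminary-effectiveness wording of Aim 2 and the text on the outcome models should be checked against it. The correction of the power figure does not depend on that.

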Intervention Overview

Clinics randomized to the intervention arm will implement the D2C strategy as described above, including Health Data Information, Active Surveillance, and Case Management with the addition of the data component. The D2C strategy will involve a 5-step process: (1) identify not-in-care PLWH using the MIS, (2) verify eligibility criteria, (3) contact patients and invite to visit the clinic, (4) determine care status and reengage into care, and (5) provide case management services and confirm engagement in care.¹²

D2C Ukraine

Steps 1 and 2 will follow the same procedure at both intervention and control sites to ensure equal conditions of study enrollment. Step 3 will be conducted using Active Outreach at the intervention sites. Steps 4 and 5 will be achieved through use of an Acuity Tool and derived Acuity Score. The Acuity Tool will be used to identify barriers to HIV care engagement, including mental health and substance abuse, and to establish referrals to other services, as described above in Overview of Data to Care Strategies.

Procedures

Patient selection and verification of inclusion criteria

A Recruiter (clinical staff authorized to access MIS at each site) will use the D2C module in the MIS to access the “Tracking Journal” which includes patients who have a confirmed HIV diagnosis, started ART, and missed their clinical appointments (medication pick-up or other). Going through the list ('New cases' or 'In progress' or 'Not tracked' sections), Recruiter reviews the MIS data (including in other modules) and identify patients who meet the following criteria:

- a) registered within the MIS as having received a positive HIV diagnosis at any time in the past
- b) missed a clinical visit (ART pick-up or other) more than 7 days ago
- c) registered with IDU as probable mode of HIV transmission, or history of IDU documented at any clinical visit
- d) not been contacted by other clinical staff after the current missed visit
- e) 18 years or older

For each patient meeting these criteria, Recruiter puts an “E” letter in the beginning of the Comment field in the Tracking Result section (before any other text in this field, separated by a space). This letter indicates that the patient is eligible for recruitment into the study and filters the Tracking Journal to display only these patients.

Patient outreach and verification of exclusion criteria

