Next, using the contact information available in the MIS and paper documentation, Recruiter attempts to contact the patients in the E-list by phone using the procedure described in the “Tracking SOP” developed by the Public Health Center. If the contact is successful, Recruiter first has to make sure that he is talking to the intended patient, without revealing that he is calling regarding HIV treatment. Once the patient (or a trustee) identity is confirmed, Recruiter asks about the reasons of the missed visit, and assesses the following exclusion criteria and takes corresponding actions:

- Patient is already re-engaged in care and visited the clinic recently
 - In this case Recruiter verifies the MIS clinical records and updates if necessary
- Patient has sufficient supply of medications (available to him for any reason)
 - Recruiter asks about the amount, and records the date of the next visit accordingly
- Patient moved to another clinic, city, country, or penitentiary institution
 - Recruiter provides information about clinics where the patient may continue treatment and initiates the formal patient transfer procedure
- Patient died
 - Recruiter initiates the de-registration procedure

In these cases, Recruiter adds a “X” letter to the Comment field (to make “EX”). All phone contact details are recorded in the MIS.

D2C Ukraine

If the contact is successful and exclusion criteria are not met, Recruiter explains why it is important to continue treatment without interruptions and informs the patient that he or she is eligible to enroll into a research study, using a standard script (Appendix 1, two versions for the study arms). Regardless of the interest in the study, Recruiter schedules patient's next visit at the earliest convenience, and records the date in the MIS. In these cases, Recruiter adds a "L" letter to the Comment field (to make "EL").

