If the first contact is unsuccessful, Recruiter adds a "R" letter to the Comment field (to make "ER"). The following contact attempts are conducted according the "Tracking SOP" – minimum three additional attempts with 1-2 weeks apart and engaging social workers and other projects if available, with additional invitation to participate in the study using the script. If the patient is reached but refuses to come to the clinic during the first contact, the status is also updated to "ER". Additional three attempts to contact and convince the patient to come are made following the same procedure. The status of the patient remains as "ER" until he agrees to come to the clinic, or the final (fourth) attempt is unsuccessful. After four unsuccessful attempts (with or without contact with the patient) the status is changed to "ERZ".

At the Intervention sites, Recruiter exports the ER-list and gives it to a Case Manager (through Data Manager). The list includes, if available, Syrex and Case++ codes (alphanumeric unique IDs used by prevention and care and support NGOs) to enable outreach through NGOs. Case Manager at the Intervention sites undertakes additional efforts to reach and recruit the patients using all available methods (phone calls, home visits [following the procedures outlined in the "Tracking SOP"], community and social networks, harm reduction and HIV-service NGOs). Up to three contact attempts (bi-weekly) will be made for each participant. The dates and results of the attempts are recorded in the online Recruitment Log (developed based on the ER-list, Annex 2). In case of a successful contact, Case Manager assesses the exclusion criteria described above, invites to participate in the study, and schedules the next visit. Recruiter monitors the Case Manager's contact attempts in the Recruitment Log bi-weekly and transfer information to the MIS, including the updates to the E-status (from "ER" to "ERX" or "ERL"). After three unsuccessful attempts by Case Manager (four total including the initial attempt by Recruiter) the status is changed to "ERZ".

Additional contacts with the patients on the EL-list may be made by Recruiter and/or Case Manager on the day before the scheduled visit to confirm the appointment and ensure the patient remembers about the visit.

First visit

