Extensive measures will be taken to ensure confidentiality. After Informed Consent is obtained, IDI participants will be assigned a study code which is the only identifier in the study database. Key informants will be assigned Study Participant Code containing no identifiable information and consisting of geographical area abbreviation, professional degree and research serial number.

If during IDIs sensitive topics emerge and there is further inquiry through targeted probes during the IDIs, every effort will be made to ensure that the level of risk to participants does not exceed minimal risk. We seek to reduce risk using several strategies often used in such settings – these include: a) asking participants never to use personal identifiers (e.g., someone's name); b) to discuss observations that they "deem" sensitive or potentially risky for them in a general way, in the third person, in terms of their "observation of others" or "stories they have heard", and refrain from providing any names or any other identifying information. We will clearly stipulate this as part of the Informed Consent, pre-amble to the IDI guide and will reinforce it during the IDI conduct. In general, the risk for Key informants is minimal. We will take measures to reduce this risk and will carefully and frequently monitor this.

D2C Ukraine

Prior to the start of each IDI the interviewer will also explain that the information that is discussed will remain anonymous and that all the information and views shared by the participant will be kept confidential. The participants will be instructed that they may choose to withdraw from the study at any point and decide not to complete the IDI activities if they feel participation causes them any distress. All participants will be able to choose a pseudonym they would like to be called throughout the study and assigned an anonymous identification code.

Quantitative data collection

Informed Consent

Written informed consent will be obtained from each study participant. One informed consent form (ICF) version will be used for both study arms.

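### Consent follows an outreach and invitation step that differs by arm, so randomising clinics does not make the enrolled patients comparable, although the plan says Steps 1 and 2 secure equal enrolment conditions

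*Combined protocol and SAP*

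**What the plan says.** Specific Aim 2 randomises clinics, not patients, within matched pairs. The Intervention Overview lists five steps: identify, verify eligibility, contact and invite, re-engage, case-manage. It says "Steps 1 and 2 will follow the same procedure at both intervention and control sites to ensure equal conditions of study enrollment", and then that "Step 3 will be conducted using Active Outreach at the intervention sites".

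The detailed procedures add the following:

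- **First call, both arms.** A Recruiter phones patients listed from the MIS. On contact, "Recruiter asks about the reasons of the missed visit, and assesses the following exclusion criteria and takes corresponding actions". Those not excluded are told about the study "using a standard script (Appendix 1, two versions for the study arms").
- **Not reached or refusing (ER status), general procedure.** The Tracking SOP applies: "minimum three additional attempts with 1-2 weeks apart and engaging social workers and other projects if available".
- **ER status, intervention sites.** The ER-list goes to a Case Manager. "Case Manager at the Intervention sites undertakes additional efforts to reach and recruit the patients using all available methods". On contact, "Case Manager assesses the exclusion criteria described above, invites to participate in the study, and schedules the next visit".
- **Consent.** It is taken by an Interviewer at the first clinic visit, after all of the above. On the form itself, "One informed consent form (ICF) version will be used for both study arms" (Quantitative data collection, Informed Consent).

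Under Data Collection, engagement, ART (re-)initiation and viral suppression are all timed from enrolment, and the analysed sample is the 160 enrolled. Under Statistical Analysis and Feasibility Assessment, the later RCT counts as feasible if the arms differ by 22% on engagement in HIV care.

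**The concern.** In a cluster trial, randomisation balances clinics. It balances patients only if the way they enter the study does not depend on the arm. Here a patient becomes one of the 160 by returning to the clinic and consenting, and what brings the patient back differs by arm. Staff know the allocation at that stage, since the script and the staffing are arm-specific.

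If patients recruited through additional outreach have a different prognosis from those who agree at the first call, the arms will differ in case mix before any case management starts. That difference would enter the primary comparison, the 22% rule, and the effect size that the pilot is meant to supply for the RCT sample size.

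The concern is not that outreach differs; outreach is part of the strategy. It is that the clock starts after the patient has returned. The comparison therefore inherits the case mix that outreach creates without counting the return that outreach achieved.

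**Working it through.** **1. What is common before consent, and what is not**

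| Element before consent | Control sites | Intervention sites |
|---|---|---|
| MIS listing, inclusion criteria | Recruiter | Recruiter, same |
| Exclusion list | same | same |
| First call and its exclusion check | Recruiter | Recruiter, same |
| Script for the invitation | control version | intervention version |
| Re-contact of ER patients | Tracking SOP procedure, social workers if available | Case Manager, additional methods |
| Exclusion check and invitation of ER patients | Recruiter's procedure | Case Manager |
| Nominal number of attempts before closing (ERZ) | four | four |
| Consent form | one version | same |

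For patients who agree at the first call, the documented pre-consent differences are the script version and, possibly, a day-before reminder from a Case Manager. For ER patients, the mode, the intensity and the person differ as well. Part of Step 2 (the exclusion half of eligibility) is carried out inside Step 3, so for ER patients even Step 2 is not done the same way in both arms.

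**2. The plan's own figure**

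Inputs from Sample size: 50% versus 72%, significance level 0.05 (two-sided assumed), 80 per arm. Clustering is ignored here. With z = 1.96, n = 80 and mean proportion 0.61:

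- Null SE = √(2 × 0.61 × 0.39 / 80) = 0.0771
- Alternative SE = √((0.50 × 0.50 + 0.72 × 0.28) / 80) = 0.0751
- Power = Φ((0.22 − 1.96 × 0.0771) / 0.0751) = Φ(0.916) = 82.0%

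Exact power of the Pearson chi-square test is 81.6%. The stated 80% with 160 patients is reproduced, so the point rests on no arithmetic error in the plan.

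**3. Illustration of possible size (assumed inputs)**

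The documents give no yield or outcome by recruitment route, so q and d below are assumptions. Let q be the share of the intervention arm that enrols only through extra outreach, with no counterpart among enrolled controls. Let d be the amount by which their success probability is lower. The true effect is 22 points for every type of patient, and control is 50%. The Sample size section gives 50% and 72% for ART re-engagement; using them for the engagement rule is a further assumption.

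Observed difference = 22 − 100 × q × d points.

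| q | d | Observed difference | Power at 80 per arm | Two-sided rejection rate if no true effect |
|---|---|---|---|---|
| 0 | 0 | 22 | 82% | 5% |
| 0.2 | 0.2 | 22 − 4 = 18 | 64% | 8.0% |
| 0.3 | 0.2 | 22 − 6 = 16 | 54% | 11.8% |

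If the sign of d were reversed, the same arithmetic would raise the observed difference: a true effect of 18 or 16 points would show as 18 + 4 = 22 or 16 + 6 = 22 and meet the rule.

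**4. Protection in the analysis**

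The mixed model adjusts for sex/gender, age and baseline covariates found to differ across sites, and examines substance use severity and ART history. Recruitment route is not among the named covariates. The implementation section lists recruitment rate and contact-attempt measures as process outcomes, but nothing ties them to the outcome comparison.

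**The case against.** The plan limits its statement of sameness to Steps 1 and 2 and openly says in the next sentence that Step 3 differs. That stands: only the purpose clause, that this secures equal enrolment conditions, is too strong.

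Control sites are not passive. The general procedure requires further attempts with social workers where available, home visits by Case Managers follow the same Tracking SOP, and both arms close a case after four attempts. A reader might infer that control sites do no comparable re-contact. The documents do not support that: the SOP is not included, so the contrast is one of mode, intensity and person, of unknown size.

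The script texts are not shown, so they may differ only slightly. The exclusion list is identical, and a different person applies it only to ER patients at intervention sites. Covariate adjustment includes plausible prognostic factors. All of this narrows the concern and leaves it standing. Entry still depends on arm, and measured covariates can correct case mix only in part.

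On the remedy, patients with ES status are themselves a subset defined after randomisation. They exclude the hard-to-reach patients whom the strategy targets, and at intervention sites they may get Case Manager reminders. A comparison in ES patients is therefore a sensitivity analysis and should not displace the all-enrolled one.

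**Conclusion.** The point holds as a limit on what randomisation protects. Enrolment follows an arm-specific step, so comparability of the 160 cannot be assumed, and the plan's sentence on equal enrolment conditions goes further than its own procedures allow.

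A reader might go on to infer that the enrolled groups are in fact not comparable, or that the intervention effect will be understated. The documents support neither. They contain no enrolment data, no yields by route and no script texts, so neither size nor direction can be established. The 16 to 18 points above depend wholly on the assumed 20% to 30% share and 20-point prognosis gap, with clustering ignored. They show only that a modest imbalance could decide whether the 22% rule is met. The sponsor should address this before recruitment starts, or before analysis if recruitment has begun.

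**What to change.** 1. Use one common invitation script at first contact in both arms, as is already done for the consent form.
2. Report the flow through the MIS status codes (E, EX, EL, ER, ERX, ERL, ERZ, ES, ERS) by clinic and arm.
3. Keep the all-enrolled comparison as primary. Beside it, pre-specify as a sensitivity analysis the primary-outcome comparison in ES (first-contact) patients only. State that ES is a smaller post-randomisation subset and that Case Manager reminders may still differ between arms.
4. Reword the Intervention Overview to say that only MIS listing against the inclusion criteria and the Recruiter's first call are common to both arms.

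**Cost.** One shared script, one table, one added analysis and one sentence. The status is already recorded at the first visit, so no new data are needed. The sensitivity analysis loses precision: on the illustrative shares, ES patients in the intervention arm would number 80 × 0.8 = 64 or 80 × 0.7 = 56. The total would be at most 144 or 136, and fewer if control sites also enrol re-contacted patients.
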